8.8.2.9. Modified Medical Research Council Dyspnea Score (MMRC)

The Modified Medical Research Council scale (MMRC scale) is a simple grading system largely used in the assessment of dyspnea in chronic respiratory diseases, such as IPF or COPD. The MMRC breathlessness scale comprises five statements that describe almost the entire range of respiratory disability from "None" (Grade 1) to "Almost complete incapacity" (Grade 5).

Table 5: Modified Medical Research Council Dyspnea Scale

The Modified Medical Research Council (MMRC) Dyspnoea Scale

Grade of dyspnoea	Description
0	Not troubled by breathlessness except on strenuous exercise
1	Shortness of breath when hurrying on the level or walking up a slight hill
2	Walks slower than people of the same age on the level because of breathlessness or has to stop for breath when walking at own pace on the level
3	Stops for breath after walking about 100 m or after a few minutes on the level
4	Too breathless to leave the house or breathless when dressing or undressing

8.8.2.10. ATAQ-IPF questionnaire

ATAQ-IPF questionnaire is designed to determine how IPF affects the patient's quality of life. There are 13 sections and a total of 74 questions to answer from "Strongly disagree" (Grade 1) – "Strongly agree" (Grade 5). The full ATAQ-IPF questionnaire is found in Appendix 3.

8.8.2.11. Worsening IPF

Worsening IPF is defined as acute IPF exacerbation, hospitalization due to respiratory symptoms, IPF related fatal events, or lung transplantation.

8.8.2.12. Adverse Event (AE) Monitoring

The PI or a qualified designee listed on Form FDA 1572 must assess the severity and relationship to study medication for all AEs (see Section 12.2).

All observed or volunteered AEs regardless of treatment group or suspected causal relationship to the investigational product(s) will be recorded on the AE page(s) of the CRF.

Each PI and research team are responsible for identifying adverse events and reporting them.

For all AEs, the Investigator must pursue and obtain information adequate to determine the outcome of the AE and to assess whether it meets the criteria for classification as an SAE (see Section 5) requiring immediate notification to the Sponsor or its designated representative.

For all AEs, sufficient information should be obtained by the Investigator to determine the causality of the AE. The Investigator is required to assess causality and indicate that assessment on the CRF. For AEs with a causal relationship to the investigational product, follow-up by the Investigator is required until the event or its sequelae resolve or stabilize at a level acceptable to the Investigator, and Sponsor concurs with that assessment.

Adverse events (serious and non-serious) including all suspected unexpected serious adverse reactions (SUSARs) should be recorded on the CRF from the date of informed consent until the end of their participation in the study (i.e., the subject has discontinued or completed the follow-up visit).

8.8.2.13. Laboratory Evaluations

Laboratory evaluations will include the tests listed in Appendix 1.

9. STUDY DRUG MATERIALS AND MANAGEMENT

9.1. Study Drug

Table 6: Study Drug Information

Investigational Drug:	MN-001 or matching placebo
Formulation:	250 mg tablet (MN-001) or matching placebo
Frequency:	250 mg 3 tablets (750 mg) bid, 2 tablets (500 mg) tid, or matching placebo
Storage Conditions:	Store at room temperature

9.2. Study Drug Packaging and Labeling

At a minimum the following information will be included on each bottle:

- Name of Sponsor
- Study number/Acronym/IND number
- Route of administration
- Quantity of dosage unit
- Directions for use
- Storage conditions
- Space for information to be completed by Investigator/designee:
 - o Name and telephone number of Investigator
 - Dispensing date
 - Subject number
- Statement "Caution: New Drug Limited by federal law to investigational use"
- Statement: "Keep out of reach of children"

9.3. Study Drug Storage

The clinical study drug MN-001 should be stored at room temperature (preferably 18-23^oC, but 15-25^oC is acceptable).

9.4. Study Drug Administration

The study drug will be dispensed by appropriately qualified site study staff as indicated on the delegation of authority log. Subjects will self-administer the study drug at home except on clinic visit days (Day1, Months 1, 3, 6, 7, 9 and 12). On those days, subjects will be instructed to wait until they come to the clinic to take their study medication. The subject will be instructed to return all unused study drug to the clinical trial site at each visit.

9.5. Study Drug Accountability

Investigational clinical supplies must be received by the PI or a designated person at the study site, handled and stored safely and properly, and kept in a secured location to which only the Investigator and/or designated assistants have access. Clinical supplies are to be dispensed only in accordance with the protocol.

The PI or designee is responsible for keeping accurate records of the clinical supplies received from the Sponsor or designee, the amount dispensed to and returned by the subjects, and the amount remaining at the conclusion of the study. At the end of the study, all clinical supplies must be returned to the Sponsor, or designee, after confirmation with the CRA (Clinical Research Associate) or destroyed at the clinical site. Study drug will not be destroyed until written documentation is received from the study sponsor or designee. Proper documentation of the destruction of study drug must be provided by the site.

The following information is to be included in the CRF: visit medication dispensed, dosing start/stop dates, dosage level, number of tablets dispensed and number of tablets returned.

10. EFFICACY ASSESSMENTS

Efficacy will be assessed by the following:

- Absolute and relative change from baseline of FVC and FVC% predicted up to 26 weeks
- Semiannual decline on disease activity based on FVC
- Annual/semiannual decline on disease activity based on the 6-minute walk test (6MWT)
- Modified Medical Research Council Dyspnea Score (MMRC)
- Quality of life (QOL) measured by A Tool to Assess Quality of Life in Idiopathic Pulmonary Fibrosis (ATAQ-IPF)
- Frequency of worsening IPF
- Time to first worsening IPF

11. SAFETY AND TOLERABILITY ASSESSMENTS

Safety will be assessed by the proportion of subjects with the following events:

- Clinical and laboratory treatment emergent adverse events (TEAEs)
- Discontinuations due to TEAEs
- Treatment emergent serious adverse events (TESAEs)

Safety (relationship and severity) and tolerability will further be assessed by statistical and clinical review of AEs, laboratory values, ECGs, physical examinations, vital signs and weight.

12. ADVERSE EVENTS

12.1. Definition of Adverse Events

An AE is any untoward medical occurrence in a study subject administered a medicinal (investigational) product and which does not necessarily have a causal relationship with this treatment. An AE can therefore be any unfavorable and unintended sign (including a clinically significant abnormal laboratory finding), symptom, or disease temporally associated with the use of a medicinal (investigational) product, whether or not considered related to the medicinal (investigational) product. Adverse events may include the onset of a new illness and the exacerbation of pre-existing conditions.

Other untoward events occurring in the framework of a clinical study are also to be recorded as AEs, (e.g., those occurring during treatment-free periods, including screening or post-treatment follow-up periods), in association with study-related procedures and assessments or under placebo.

12.2. Assessment of Adverse Events

The PI or an authorized physician will assess all AEs for severity, relationship with study medication, and whether it meets the criteria for classification as a SAE, requiring immediate notification to the Sponsor or designee (see Section 12.5). These assessments will be made in accordance with the standard ratings detailed in the following sections.

12.2.1. Severity Assessment

The severity of AEs will be determined as described in Table 7.

Table 7: Adverse Events Severity Definition

Mild Grade 1	Ordinarily transient symptoms that do not influence performance of subject's daily activities. Treatment is not ordinarily indicated.
Moderate Grade 2	Marked symptoms sufficient to make the subject uncomfortable. Moderate influence on performance of subject's daily activities. Treatment may be necessary.
Severe Grade 3	Symptoms cause considerable discomfort. Substantial influence on subject's daily activities. May be unable to continue in the study and treatment may be necessary.
Life- threatening Grade 4	Extreme limitation in activity, significant assistance required; significant medical/therapy intervention required hospitalization probable.
Death Grade 5	Death.

When changes in the intensity of an AE occur more frequently than once a day, the maximum intensity for the event should be noted for that day. Any change in severity of signs and symptoms over a number of days will be captured by recording a new AE, with the amended severity grade and the date (and time, if known) of the change.

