#### 14.1. Adverse Events

Adverse events (AEs) will be coded using the Medical Dictionary for Regulatory Activities (MedDRA) central coding dictionary, version 21.0.

Summary tables for AEs will include treatment-emergent adverse events (TEAEs, defined as AEs occurred during or after the first administration of a study drug). AEs occurred before the first administration of a study drug will be listed separately. Aes occurring 7 days after the last dose of study medication will be listed separately.

Unless otherwise stated, AE analyses will be subject-based, each subject will be counted once in frequency tables at the subject, SOC and preferred term levels, and the denominator for percentages will be the number of subjects in the SAS, in the respective treatment arm (i.e. "as treated" assignment of treatment arms).

AEs will be assigned to study phases (DBT or OLE) based on their start date.

If the start date of an AE is incomplete:

a/ If only day is missing, and if in the same month the treatment was started then the start date of AE will be imputed with the day of first treatment. If treatment started earlier and not in that month then the first day of the month will be used for imputation.

b/ If month and day are missing, and the treatment start date was in the same year then the start date of AE will be imputed with the month and day of the first treatment administration. If the treatment start date was in the previous year, then 01 JAN will be used for imputation.

c/ If the entire AE start date is missing then the date will not be imputed, but the AE will be considered treatment-emergent.

If the end date of an AE is missing, the AE will be considered as "ongoing".

If a subject xperiences a TEAE with a missing causality assessment, then relationship will be categorized as "Related". AEs with a missing causality assessment during the screening period relationship will be categorized as "Unrelated".

If a subject experiences a TEAE with a missing severity assessment, then severity for this TEAE will be categorized as "Severe".

In addition to keeping the 5-level categorization of causality of AEs, they will also be dichotomized into two categories: related/not related. "Related" category comprises events which were classified by the investigator as possibly, probably or related to treatment, whereas "Not Related" category comprises the other two levels of the investigator's assessment ("Unlikely to be related" and "Unrelated").

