#### 14.1.1. All Adverse Events

An overview of number of subjects (%) with treatment-emergent AEs will be presented for the main AE categories (All AEs, AEs leading to discontinuation, SAEs, SAEs leading to discontinuation, AEs with at least Grade 3 severity (Severe AEs, Life-threatening AEs, Deaths), AEs and SAEs with relationship to IMP as possibly related, probably related, or related) by treatment arm and phase.

The number (%) of subjects with treatment-emergent AEs will be presented by phase, treatment arm, System Organ Class and Preferred Term (MedDRA), AE severity, and relationship to study drug (for both AEs and SAEs). Each subject will be counted only once within each preferred term per study phase. If a subject experiences more than one AE within a preferred term for the same recording phase, only the AE with the strongest relationship or highest severity, as appropriate, will be included in the summaries by relationship and severity.

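### An adverse event that merely eases after Visit 8 is re-recorded and counted again in the open-label phase, so former-placebo subjects acquire events on MN-001 that began on placebo

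*Protocol*

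**What the plan says.** Recording. Protocol 12.2.1 requires: "Any change in severity of signs and symptoms over a number of days will be captured by recording a new AE". That follow-on entry does not keep the original onset date; it is made "with the amended severity grade and the date (and time, if known) of the change". The rule is not limited to worsening. Only changes within one day are exempt; for those, the day's maximum is noted.

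Classification. SAP 14.1 states: "AEs will be assigned to study phases (DBT or OLE) based on their start date". Its TEAE definition reads: "TEAEs, defined as AEs occurred during or after the first administration of a study drug". It sets no condition that the event be new or worse than before. SAP 10.2 starts the OLE on the day after Visit 8. SAP 10.1 labels placebo subjects who cross over as Former Placebo, and they then take MN-001.

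Counting. SAP 14.1.1 states: "Each subject will be counted only once within each preferred term per study phase". SAP 14 analyses safety separately for the two phases.

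Pre-dose events. Protocol 8.8.2.12 says that AEs "should be recorded on the CRF from the date of informed consent until the end of their participation in the study". Protocol 12.1 also includes screening-period events, and SAP 14.1 expects them: "AEs occurred before the first administration of a study drug will be listed separately". Protocol 12.3 instead starts collection at first dose.

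**The concern.** The recording rule and the classification rule do not fit together. The protocol splits one episode into several AE records, each with its own date. The SAP then treats every record as a separate event and places it by that date. No rule ties a follow-on record to the original onset across Visit 8 or across first dose, and de-duplication stops at the phase boundary. An improvement can therefore appear in the tables as a new event.

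The move from placebo to MN-001 at Visit 8 is where this matters most. A reader of the OLE tables will take an event in the Former Placebo column as one that began on MN-001. The severity summaries are exposed too: a Grade 4 DBT event that eases to Grade 3 after Visit 8 enters the OLE count of events of Grade 3 or worse.

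The SAP already uses the missing principle elsewhere. Its laboratory shift tables in 14.3 are confined to clinically significant findings that are new or have worsened since baseline.

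**Working it through.** The plan gives no figure to reproduce. The check applies the written rules to example records and then works out the weight of one subject.

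**Inputs.** About 15 subjects randomised 2:1 (Protocol synopsis): 15 × 2/3 = 10 on MN-001 and 15 × 1/3 = 5 on placebo. First dose is Day 1. Visit 8 is set at Day 183 for illustration. The example events are invented, and none resolves between its two records.

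| Subject | Records (grade, day) | Counted as written | Counted under the rule proposed below |
|---|---|---|---|
| Placebo, diarrhoea | Grade 2, Day 150; Grade 1, Day 190 | DBT Placebo and OLE Former Placebo | DBT Placebo only |
| MN-001, nausea | Grade 2, Day −4; Grade 1, Day 5 | Pre-dose listing and DBT MN-001 | Pre-dose listing only |
| Placebo, nausea | Grade 2, Day −4; Grade 1, Day 5 | Pre-dose listing and DBT Placebo | Pre-dose listing only |

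For the first subject, the Day 190 record is a new AE (Protocol 12.2.1). It starts after Day 183, so it belongs to the OLE (SAP 14.1 and 10.2). It follows first dose, so it is a TEAE. It is the only OLE record of that term, so the once-per-phase rule does not remove it. An MN-001 subject with the same two dates would be counted in DBT and again in OLE. That is double counting across phases, because the event did begin on MN-001.

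The second and third subjects show that the pre-dose route works the same way in both randomised arms. It arises only if pre-dose AEs are collected.

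**Weight of one subject, for one preferred term in one phase.**
- Former Placebo, OLE: 1/5 = 20 percentage points.
- MN-001: 1/10 = 10 percentage points.
- Placebo, DBT (pre-dose route): 1/5 = 20 percentage points.

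The addition is zero if the subject has another genuine event of that term in that phase.

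**Chance of at least one affected subject.** The documents give no rate, so the per-subject probability p is assumed. The chance is 1 − (1 − p)^n.

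| Assumed p | n = 5 | n = 10 |
|---|---|---|
| 5% | 23% | 40% |
| 10% | 41% | 65% |
| 20% | 67% | 89% |
| 30% | 83% | 97% |

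For example, 1 − 0.95^5 = 0.226 and 1 − 0.95^10 = 0.401.

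**The case against.** The strongest reply is that one link is inferred. Protocol 12.2.1 gives the new record the date of change but does not call it a start date, and Protocol 12.3 separately asks for the date of onset. The SAP author reviewed the CRFs (SAP 4), which are not in the documents. TEAE status by start date is also inferred, from the definition and from the date-imputation rules, such as "If the entire AE start date is missing then the date will not be imputed, but the AE will be considered treatment-emergent". Phase by start date, however, is explicit, and a new AE whose only stated date is that of the change would ordinarily start then. The inference is reasonable, and checking the CRF would settle it.

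A second reply is that little turns on it. The SAP plans no inferential test on AEs and no contrast of OLE Former Placebo with DBT Placebo. Severity tables would show the eased record at its lower grade, and with about 15 subjects the listings allow a reader to trace continuations. This limits the harm, but the incidence tables would still be wrong.

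Three stronger readings are tempting, and the documents do not support them:
- **Easing pre-dose events count against MN-001.** They count in whichever arm the subject is in, so randomisation gives both arms the same expected inflation. They also depend on the unresolved conflict between Protocol 8.8.2.12 and 12.3. Only the Visit 8 boundary moves an event from placebo to MN-001.
- **Cough and dyspnoea are affected most.** This is not shown. Symptoms present at entry may be medical history rather than AEs, and Protocol 12.3 has a recognised condition named in place of its individual symptoms.
- **The 20 and 10 points measure the bias.** They are the weight of one subject in groups of this size and say nothing about frequency.

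**Conclusion.** The point holds at the Visit 8 boundary. The stated rules, and not merely a missing detail, count an easing placebo-phase AE again under Former Placebo on MN-001, and count an easing MN-001 event in both phases. Each affected subject adds about 20 points (1 of about 5) or about 10 points (1 of about 10) to that preferred term, at most once per term per phase. The frequency is unknown.

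This rests on reading the date of change as the new record's start date, and on the planned size and allocation being met. The pre-dose route is conditional on AE collection from consent and affects both arms. The change should be made because the tables would otherwise misstate when events began and the correction is cheap. No planned hypothesis test is affected.

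**What to change.** Add to SAP 14.1:

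1. Records of the same preferred term in one subject that are contiguous, with no resolution between them, form one event. The start date of the first record sets TEAE status and phase.
2. A later record within that linked event counts as treatment-emergent only if its grade exceeds the event's worst grade before first dose. It counts as new in the OLE only if its grade exceeds the event's worst grade before the first OLE dose.
3. An event that resolved and then recurred is a new event at any grade.
4. All split records stay in the listings.

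Item 3 is needed because a grade comparison not confined to contiguous records could drop a genuine recurrence. For example, mild diarrhoea that resolved on placebo and returned as mild on MN-001 must still count. Diarrhoea was among the most frequent events on MN-001 in the earlier studies (Protocol 4.2.1).

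Also reconcile Protocol 8.8.2.12 with 12.3 on when AE collection begins, and confirm from the CRF which date a split record carries.

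The cost is a few sentences in the SAP and one derivation step. No new data are needed, since Protocol 12.3 already asks for onset date, outcome date and severity.

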12.2.2. Relationship to Study Drug

One of the following categories in Table 8 should be selected based on medical judgment, considering the definitions below and all contributing factors.

Table 8: Adverse Events Causality Definition

Related	A clinical event, including laboratory test abnormality, occurs in a plausible time relationship to treatment administration, and which cannot be explained by concurrent disease or other medications or chemicals. The response to withdrawal of the treatment (dechallenge ^a) should be clinically plausible. The event must be definitive pharmacologically or phenomenologically, using a satisfactory rechallenge ^b procedure if necessary.
Probably related	A clinical event, including laboratory test abnormality, occurs within a reasonable time sequence to administration of the treatment, unlikely to be attributed to concurrent disease or other medications or chemicals, and which follows a clinically reasonable response on withdrawal (dechallenge). Rechallenge information is not required to fulfill this definition.
Possibly related	A clinical event, including laboratory test abnormality, occurs within a reasonable time sequence to administration of the treatment, but which could also be explained by concurrent disease or other medications or chemicals. Information on treatment withdrawal may be lacking or unclear.
Unlikely to be related	A clinical event, including laboratory test abnormality, occurs with a temporal relationship to treatment administration that makes a causal relationship improbable, and in which other medications, chemicals, or underlying disease provide plausible explanations.
Unrelated	A clinical event, including laboratory test abnormality, occurs with little or no temporal relationship with treatment administration. May have negative dechallenge and rechallenge information. Typically explained by extraneous factors (e.g., concomitant disease, environmental factors, or other medications or chemicals).

^a Dechallenge is when a medication suspected of causing an AE is discontinued. If the symptoms of the AE disappear partially or completely, within a reasonable time from medication discontinuation, this is termed a positive dechallenge. If the symptoms continue despite withdrawal of the medication, this is termed a negative dechallenge. Note that there are exceptions when an AE does not disappear upon discontinuation of the medication, yet medication-relatedness clearly exists (e.g., as in bone marrow suppression, fixed medication eruptions, or tardive dyskinesia)

12.3. Recording Adverse Events

Adverse events should be collected and recorded for each subject from the date that the first study dose was taken until the end of their participation in the study (i.e., the subject has discontinued or completed the study). Only those AEs that occurred while on study drug that have not been resolved will be followed until resolution or stabilization.

Following the end of the subject's participation in the study, the PI or an authorized delegate should report SAEs "spontaneously" if considered at least possibly related to study medication.

Adverse events may be volunteered spontaneously by the study subject, or discovered by the study staff during physical examinations or by asking an open, non-leading question such as, "How have you been feeling since you were last asked?" All AEs and any required remedial action will be recorded in the subject's source documentation and transcribed onto the appropriate CRF page for the study period indicated. The nature of AE, date (and time, if known) of AE onset, date (and time, if known) of AE outcome to date, severity, and action taken of the AE will be documented together with the PIs or an authorized physician's assessment of the seriousness of the AE and causal relationship to study medication and/or study procedure (at the time of assessment).

All AEs should be recorded individually in the study subject's own words (verbatim) unless, in the opinion of the PI or an authorized physician, the AEs constitute components of a recognized condition, disease, or syndrome. In the latter case, the condition, disease, or syndrome should be named rather than each individual symptom. The AEs will subsequently be coded using the MedDRA.

